#### 6.5. Analysis of Percent Change in Lesion Count

The percent change in lesion count will be analyzed using a CMH test using ridit scoring. The resulting test statistics for the row-mean scores difference from the CMH analysis will be combined using the procedure by Rubin (1987) and Li et al. (1991) to produce a pooled CMH statistic and p-value.

#### 6.6. Missing as Failure Analysis of Lesion Counts

The missing-as-failure analysis will be used for lesion counts to impute missing lesion count change from baseline at week 12.

For missing facial lesion count data, the median change from baseline in lesion counts from among all observed IGA failures at Week 12 will be substituted. For missing truncal lesion count data, the median change from baseline in lesion counts from among all observed PGA failures at Week 12 will be used.

In both cases the median will be calculated separately for each treatment group, using actual treatment, and the imputation will use the median that corresponds to the treatment group of the subject being imputed.

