	Screening Visit 1 (maximum 14 days+3 days prior to Baseline)	Baseline Visit	Week 1 Visit (±3 days)	Week 2 Visit (±3 days)	Week 4 Visit (±3 days)	Week 8 Visit (±3 days)	Week 12 Final/ET Visit ² (±5 days)
Skin Oiliness Scale (SOS) Questionnaire ¹¹		X					X
Self-assessment of facial acne improvement							X
Study drug(s) Dispensing (D) and Accountability (A)		D			D/A	D/A	A
Moisturizer/cleanser Dispensing (D)		D ¹⁰					
Dosing calendar Dispensed (D) returned and reviewed (RR)		D	RR	RR	RR	RR	RR
Exit Form ¹¹							X

- (1) Baseline visit must be performed maximum 14 days after Screening with a time window of +3 days. For women of childbearing potential, there must be at least 14 days between Screening and Baseline visits (for UPT reason). No re-screening will be allowed.
- (2) Week 12 procedures will be performed earlier in case of study discontinuation.
- (3) Confirm information at Baseline
- (4) For subject of childbearing potential only: Urine Pregnancy Tests will be performed at Screening, Baseline, Week 4, Week 8, Week 12. For pre-menstrual subjects re-confirm pre-menses status at every visit and in case of status change collect information on contraceptive method and perform a UPT. For the ones who begin menses after the Screening visit, urine pregnancy tests will be performed at the visit where there was a change in status and according to the schedule for females of childbearing potential (Baseline, Week 4, 8, 12/ET). Additional UPTs may be performed at the investigator's discretion.
- (5) Subjects 9 to 11 years of age who did not meet the criteria for moderate truncal acne at Baseline: PGA will be evaluated after baseline to allow the investigators to decide to start the treatment on the trunk if the subject develops truncal acne during the study whatever the PGA grade. Local tolerability will be assessed. The Lesion counts will not be evaluated.
- (6) Photos are not mandatory; subjects will be able to participate in the study even if they refuse to participate in photo procedures.
- (7) Collection of Adverse Events will begin after signing of the informed consent/assent form.
- (8) Medication that continues after Screening visit should be recorded on the Concomitant Medication page of the eCRF. Medical or surgical procedures occurring after Screening visit should be recorded on the Procedures page of the eCRF

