# 6 SAMPLE SIZE CONSIDERATION

The assumptions used to power this study are based on the Phase 2 study (SPR.18223) on the Non-Japanese population. Success rates based on IGA are assumed 23% (CD5789) and 15% (Vehicle). For a 90% power to detect a significant difference versus vehicle using a two-sided test at a type I error of 0.05, 504 subjects per arm are needed for analysis.

Based on the results from statum 1 in the phase 2 study (SPR18223), the mean difference between the active and vehicle is estimated at 3 inflammatory lesions and 6 non-inflammatory lesions. Standard deviation of changes in lesion counts, based on phase 2 and on large phases 3 trials from other projects are estimated at 12 for inflammatory lesions and 20 for non-inflammatory lesions. Using these as assumptions and a sample of 504 evaluable subjects per arm, power is 95% at least for both lesion types.

Galderma R&D RD.06.SPR.18252 Page 12 of 25

To compensate for drop-outs and non-evaluable subjects (estimated at 16%), a total of 1200 subjects are to be randomized into each treatment group in a 1:1 ratio stratified by center, with 600 subjects in each treatment group randomized.

The assumptions for truncal acne being the same as for facial acne in terms of efficacy, therefore it is estimated that the power for truncal acne is adequate.

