† P=Primary approach; S=Supportive approach ITT = Intention to Treat, ITTT = Intention to Treat for the truncal acne; PP = Per Protocol on the face; PPT = Per Protocol on the trunk; MI = Multiple imputation using the missing at random assumption; MI (MNAR) = Multiple imputation using the missing not at random assumption; LOCF=Last

Galderma R&D RD.06.SPR.18252 Page 15 of 25

Observation Carried Forward. CMH: Cochran-Mantel-Haenszel test stratified by analysis center. CMHS: Cochran-Mantel-Haenszel test stratified by analysis center using the RIDIT score. ANCOVA: Analysis of Covariance model including treatment, analysis center, and baseline lesion count as factors.

As the primary efficacy endpoint consists of 3 co-primary endpoints, all of which need statistical significance for the primary efficacy endpoint to be successful, there is no need for Type I error adjustment for the multiple comparisons of the 3 co-primary efficacy endpoints.

The study will be declared positive if the two-sided p-values is statistically significant (< 0.05) for the difference between the 2 treatment groups in all 3 co-primary efficacy endpoints, and the superiority of CD5789 50  $\mu$ g/g to Vehicle will be established.

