#### Statistical method

• IGA Success Rate:

Success rate at Week 12 based on the IGA will be analyzed using the Cochran Mantel Haenszel (CMH) test stratified by analysis center (see definition in Section 7.4.2.4). The primary analysis will be performed using the overall ITT population based on the Multiple Imputation methodology (MI) as the primary imputation method for missing values, see Section 7.4.2.2.

The p-value for the treatment comparison will be generated from the general association statistic of the stratified CMH test. Difference in success rate between treatment groups (CD5789 50  $\mu$ g/g – Vehicle) and the 95% confidence interval of the difference will be based on the large sample approximation method for binary data. The success rate for each treatment group will also be displayed for the overall ITT population.

The treatment-by-analysis center interaction for success rate will be assessed for the overall ITT population by using the pair-wise Breslow-Day tests for homogeneity of the odds ratio across analysis centers at Week 12 at alpha level of 0.10. The consistency of the treatment effect across analysis centers will be evaluated using descriptive statistics and using graphical methods.

Facial Lesion Counts:

Changes from baseline in facial lesion counts at Week 12 will be analyzed separately by type (inflammatory and non-inflammatory) using an ANCOVA (Analysis of Covariance) model including baseline count, analysis center, and treatment as factors. The primary analysis will be performed using the overall ITT population using the primary imputation method for missing values.

The p-value for the treatment comparison, estimate of the LSMEANS treatment difference (CD5789 50  $\mu$ g/g – Vehicle), and the 95% confidence interval of the LSMEANS difference will be generated from the ANCOVA model.

The treatment-by-analysis centers and the treatment-by-baseline lesion counts interactions for Change in Lesions Counts will be assessed separately by the interaction term at Week 12 at alpha level of 0.10 for the overall ITT population. The consistency of the treatment effect across

Galderma R&D RD.06.SPR.18252 Page 16 of 25

analysis centers will be evaluated using descriptive statistics and using graphical methods. The consistency of the treatment effect by baseline lesion counts will be evaluated using graphical methods.

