#### Sensitivity analyses

The above primary efficacy analysis will be repeated using the PP population using the primary multiple imputation method for missing values.

To assess the robustness of the primary efficacy result, the following sensitivity analyses will be conducted for each of the 3 co-primary efficacy endpoints (see Section 4.1) using the ITT population:

a. The same imputation method above will be repeated based on the Pattern-Mixture Model under the missing not at random (MNAR) assumption, by using the profiles from vehicle subjects with observed data to impute missing data.

b. LOCF (Last observation carry forward) approach

c. Subjects with missing IGA data at Week 12 will be considered as 'failures' for IGA success rate; and subjects with missing lesion counts data at Week 12 will be assigned the median change of lesion counts data from subjects who are 'failures' of IGA success within the same treatment group.

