c. Subjects with missing IGA/PGA data at Week 12 will be considered as 'failures' for IGA/PGA success rate; and subjects with missing lesion counts data at Week 12 will be assigned the median change of lesion counts data from subjects who are 'failures' of IGA/PGA success within the same treatment group.

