## 7.7 Analysis visit definition

All efficacy variables and local tolerability variables will be summarized and analyzed by analysis visit. Analysis visit will be imputed according to the following algorithm to summarize the data by proper visit window interval. Study day is calculated as visit date minus the date of first application plus 1.

Table 4 Analysis Visit and Visit Window				
Analysis Visit	Analysis Visit Number in Derived Dataset	Target Study Day	Visit Window (Study Day)	
Baseline	1	1	[<=1]	
Week 1	2	8	[2-11]	
Week 2	3	15	[ 12 – 21 ]	
Week 4	4	29	[ 22 – 42 ]	
Week 8	5	57	[ 43 – 70 ]	
Week 12	6	85	>70	

If multiple measurements are taken in the same interval, the one closest to the target study day will be used for the analysis. If two measurements are taken with equal differences in timing compared with the target date, the nominal visit number (recorded on the CRF page) will used.

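### The supportive missing-as-failure lesion-count analysis treats an estimated fill value as known, so its standard error is too small by about the share missing (low priority)

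*SAP*

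**What the plan says.** SAP 7.4.1.1, Sensitivity analyses, item (c), counts a missing Week 12 IGA as a failure. A subject without Week 12 lesion counts "will be assigned the median change of lesion counts data from subjects" who failed on IGA in the same arm. Section 7.4.2.2(c) repeats the rule for face and trunk, with failures taken as those "of IGA/PGA success within the same treatment group". Section 6.6 of the addendum to the SAP (final, 23 October 2017) restates it for the face: "the median change from baseline in lesion counts from among all observed IGA failures at Week 12 will be substituted". PGA failures are used for the trunk. The addendum computes the median separately by actual treatment.

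Table 1 in 7.4.1.1 lists Missing as Failure on the ITT population (ITTT for the trunk), with ANCOVA for lesion counts. Its footnote reads "P=Primary approach; S=Supportive approach", and this row is marked S. The lesion-count analysis is done "using an ANCOVA (Analysis of Covariance) model including baseline count, analysis center, and treatment as factors", and its output includes a p-value and a 95% confidence interval. Repeated draws and pooling with MIANALYZE are specified only for the multiple-imputation analyses (SAP 7.4.2.2, addendum 6.2 and 6.3). No variance correction is given for the median fill.

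Neither document states an expected share of missing Week 12 counts. SAP Section 6 allows 16% for drop-outs and non-evaluable subjects together. Note 2 to the protocol's schedule of assessments says "Week 12 procedures will be performed earlier in case of study discontinuation". SAP 7.7 says "Analysis visit will be imputed according to the following algorithm to summarize the data by proper visit window interval", and any assessment after study day 70 counts as Week 12.

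**The concern.** The fill value is a statistic computed from the same arm's data and would differ if the trial were repeated. Once it is written into the dataset, the ANCOVA treats the filled subjects as observed and ignores that variation. The reported SE therefore falls as more data go missing, while the true SE rises.

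At stake are the confidence interval and p-value of one robustness check. A reader who compares this row with the primary analysis would see an interval that is too narrow and could overrate the robustness of the result.

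**Working it through.** **Inputs.** From SAP Section 6: 600 randomized and 504 evaluable per arm; SD of change 12 (inflammatory) and 20 (non-inflammatory); differences 3 and 6; success rates 23% and 15%; two-sided 0.05; 16% for drop-outs and non-evaluable subjects. Assumed: m = 5%, 8% and 16%, the last as an upper end.

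**The plan's own figures reproduce.** For 23% versus 15% with 90% power, pooled variance and no continuity correction, n = 504 per arm. 504 / (1 − 0.16) = 600. Lesion-count power with 504 per arm is 97.8% (3, SD 12) and 99.7% (6, SD 20), consistent with the stated minimum of 95%.

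**Why the SE is too small.** Take one arm with n subjects, SD s and share m missing.

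- *Reported variance of the arm mean.* A constant near the arm mean leaves a variance of about (1 − m)s² over n records, giving (1 − m)s²/n.
- *True variance when the constant is estimated from the arm.* If the fill moves with the observed mean, the completed mean moves with it one for one. Its variance is that of n(1 − m) observations, s²/(n(1 − m)).
- *SE ratio, reported to true.* √[(1 − m) × (1 − m)] = 1 − m.
- *True variance when the constant is fixed in advance.* The completed mean is (1 − m) × observed mean + m × constant. Its variance is (1 − m)² × s²/(n(1 − m)) = (1 − m)s²/n, equal to the reported one, so the ratio is 1.

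The error therefore comes from estimating the fill and then treating it as known. Lack of spread among the filled values is not enough to cause it.

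**Numbers.** Reported SE of the difference = s√(2(1 − m)/600). SE supported by the observed data = s√(2/(600(1 − m))). Null rejection = 2[1 − Φ(1.96(1 − m))].

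| m | SD 12: reported / supported | SD 20: reported / supported | Shortfall | Null rejection |
|---|---|---|---|---|
| 5% | 0.675 / 0.711 | 1.125 / 1.185 | 5% | 6.3% |
| 8% | 0.665 / 0.722 | 1.108 / 1.204 | 8% | 7.1% |
| 16% | 0.635 / 0.756 | 1.058 / 1.260 | 16% | 10.0% |

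If the failure median lies g SDs from the arm mean, the ratio becomes √[(1 − m)(1 + mg²)] × √(1 − m). For g between 0.25 and 0.5 the shortfall is 4.4–4.9%, 7.1–7.8% and 14.3–15.6%.

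**Simulation.** The failure median does not follow the arm mean exactly, so the approximation was checked under the null with 600 per arm, SD 12, values missing at random and 4,000 runs per setting. Assumed: skewed baseline counts (minimum 20, mean 32, SD 10), mean change −14, counts floored at 0, baseline–change correlation 0 to −0.8, lesion/IGA correlation 0.3 or 0.6, and 15% success.

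| m | Reported / true SE | Null rejection |
|---|---|---|
| 5% | 0.94–0.96 | 6.2–7.4% |
| 8% | 0.90–0.93 | 6.4–7.8% |
| 16% | 0.82–0.86 | 9.4–11.5% |

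Observed cases in these settings gave 0.98–1.02 and 4.2–6.0%. A separate simulation with 60 centers in the ANCOVA and about 19% success gave shortfalls of 4–6%, 8–10% and 15–18%, with rejection of 5.8–6.7%, 7.2–7.7% and 9.6–11.3%. Fills fixed in advance gave ratios of 0.99–1.01 and rejection of 4.7–5.3% at all three shares.

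**At the design effect (3, SD 12).** With 16% missing, the median fill reports an SE of 0.56 against a true 0.67, and its nominal 95% interval covers its own expected value in 89.6% of trials (92.1% with 8% missing). For non-inflammatory counts (6, SD 20) coverage is 90.0% and 93.1%. With 16% missing, the null is rejected in 98.9% of trials with the median fill and in 97.7% with the multiple-imputation alternative given under the fix.

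**The case against.** The strongest reply is that the fill can be read as a score assigned to missing subjects, and that conditional on its value the reported SE is correct. This settles the cause: a constant as such does no harm. It does not rescue the plan, because the value is not set in advance. It is each arm's own failure median and varies from trial to trial. A value fixed beforehand would give a correct SE, but the documents supply none.

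Second, the practical consequence is slight, and this stands. At 8% missing the reported half-width for inflammatory lesions is about 1.96 × 0.665 = 1.3 lesions. The multiple-imputation alternative widens it by at most 4% at 5% missing and 7% at 8%, or about 0.05 and 0.09 lesions.

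Third, two limits on the figures stand. Coverage is for the estimator's own expected value, not for a treatment effect that the plan defines. The shortfall is measured against the SE that the observed data support; against the SE with nothing missing it is only about m/2 (2.5%, 4% and 8%).

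Fourth, robustness does not rest on this interval alone. The vehicle-based multiple imputation under missing not at random carries its own imputation uncertainty, and LOCF is planned too. Neither corrects this interval.

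**Conclusion.** The point holds, at low priority. The interval and p-value of the missing-as-failure lesion-count analysis will be too optimistic by roughly the share missing: about 5–8% in the SE at an assumed 5–8% missing, and about 14–18% at 16%. Null rejection is then about 6–7.5% and about 10%. The mechanism follows from the SAP's wording. The size rests on m and on the simulation assumptions, none of which the documents give.

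A reader might infer three stronger things that the documents do not support:

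- *That the trial's type I error is inflated.* It is not. SAP 7.4.1.1 bases success on the three co-primary endpoints, whose primary analysis is multiple imputation. This analysis is supportive and enters no decision rule, and the conclusion at the design effect is the same either way.
- *That 16% of Week 12 counts will be missing.* Section 6 combines drop-outs with non-evaluable subjects. Early-termination assessments after day 70 also count as Week 12, although those up to day 70 do not. So 16% is an upper-end assumption.
- *That any single-value fill understates the SE.* A value fixed in advance does not.

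**What to change.** Keep missing IGA or PGA as failure. For lesion counts, amend SAP 7.4.1.1(c), 7.4.2.2(c) and addendum 6.6 in one of two ways, simplest first.

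1. Keep the median fill and report only the point estimate of the treatment difference for this analysis, without confidence interval or p-value. The cost is one sentence and the loss of the interval.

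2. If an interval is wanted, replace the rule by wording such as: *Missing Week 12 facial (truncal) lesion counts will be imputed 50 times with the MI procedure, by regression of the Week 12 count on the baseline count, with minimum 0 and seed 18252. The regression will be fitted in each randomized arm to the observed IGA (PGA) failures. The ANCOVA of Section 7.4.1.1 will be fitted to each completed dataset and the results combined with MIANALYZE.* The text should say that this replaces the failure median by a failure regression, so it is a somewhat different analysis.

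Under the simulation assumptions, option 2 gave SE ratios of 0.98–1.03 and null rejection of 4.2–5.4%. A separate 2,000-run set at 16% missing gave 0.95–1.01 and 4.9–6.8%, with observed cases in the same runs at 4.5–7.0%. The cost is a little code and intervals wider than the median-fill ones by 0–4% at 5% missing, 1–7% at 8% and 3–16% at 16%. The primary analysis does not change under either option.

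A separate minor point: addendum 6.6 forms the median by actual treatment, while SAP 5.1 analyses ITT subjects as randomized. Use the randomized arm. This affects only subjects given the wrong kit and has no bearing on the SE.

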# 5.1 Intention to Treat (ITT) Population

The ITT population is defined as any subjects who are randomized. Data from subjects included in the ITT population will be analyzed according to the treatment as randomized.

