#### 5.2 Intention to Treat on the Trunk (ITTT) Population

The ITTT population is defined as any subjects in the ITT population with moderate truncal acne at Baseline visit. In practice, this excludes from the ITT population the children between 9 and 11 years old who did not meet inclusion criterion #4 (PGA) or #5 (Truncal lesion counts) at study entry and therefore not planned to be treated on the trunk.

Subjects in the ITTT population will be analyzed according to the treatment as randomized.

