## 5.3 Safety (SAF) Population

The SAF population is defined as comprising the ITT population subjects who applied/were administered the study medication at least once.

The SAF population is used for all safety analyses, except for the local tolerability on the trunk.

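### The missing-as-failure lesion-count medians are calculated by actual treatment, although the analysis is run on populations that the SAP analyses as randomized (minor)

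*SAP*

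**What the plan says.** SAP 5.1 defines the face population broadly: "The ITT population is defined as any subjects who are randomized". It then fixes the grouping: "Data from subjects included in the ITT population will be analyzed according to the treatment as randomized". SAP 5.2 does the same for the trunk: "Subjects in the ITTT population will be analyzed according to the treatment as randomized". SAP 5.3 defines the safety population as "the ITT population subjects who applied/were administered the study medication at least once", so the SAP itself allows for randomized subjects who applied nothing.

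Missing-as-failure is one of the supportive approaches in SAP Table 1, on ITT for the face and ITTT for the trunk. SAP 7.4.1.1 (Sensitivity analyses) says "sensitivity analyses will be conducted for each of the 3 co-primary efficacy endpoints (see Section 4.1) using the ITT population", and SAP 7.4.1.2 extends the same methods to the co-secondary endpoints in ITTT. For lesion counts, SAP 7.4.1.1 and 7.4.2.2 give each subject with a missing Week 12 count the median change of failures in the same treatment group. They do not mention actual treatment.

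Section 6.6 of the addendum restates the rule and adds the basis: "In both cases the median will be calculated separately for each treatment group, using actual treatment". It continues that "the imputation will use the median that corresponds to the treatment group of the subject being imputed". Section 1 of the addendum says that its content prevails over the SAP where the two differ.

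**The concern.** One analysis appears to use two groupings. The ANCOVA compares subjects in the arm to which they were randomized, while the values imputed into it come from medians built on the product received. The addendum gives no reason for the switch, and no other section reconciles it with SAP 5.1 and 5.2.

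Two groups of subjects are touched: those who received the other arm's product, and those randomized who never applied any. The second group is likely to lack a Week 12 count and has no obvious actual treatment. The analysis exists to show whether the lesion-count results withstand dropout, so its rule should be unambiguous for exactly these subjects.

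**Working it through.** **The two clauses of addendum 6.6**

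- *Calculating the median (donors).* The text says actual treatment. There is no second reading, and this conflicts with SAP 5.1 and 5.2.
- *Assigning the median (recipients).* The text says only the subject's treatment group.
  - Reading A, actual treatment carried over from the preceding clause: a dropout on the other arm's product gets that arm's median, and a never-treated subject has no defined group.
  - Reading B, the randomized arm, as ITT/ITTT implies: both kinds of subject get the median labelled with their own arm, and only the donor problem remains.

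**Planning inputs (SAP section 6)**

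The plan gives no figure for this rule, so its planning values set the scale: success 23% and 15%; lesion differences 3 (inflammatory) and 6 (non-inflammatory); SDs 12 and 20; 504 evaluable and 600 randomized per arm; 16% dropout or non-evaluable. The plan's own figures reproduce:

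- n per arm = [1.960·√(2·0.19·0.81) + 1.282·√(0.23·0.77 + 0.15·0.85)]² / 0.08² = 503.3, rounded up to 504.
- 504 / (1 − 0.16) = 600.

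**Yardstick**

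The SE of the treatment difference, SD·√(2/600), is 12·√(2/600) = 0.69 inflammatory and 20·√(2/600) = 1.15 non-inflammatory.

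**Recipients under Reading A**

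Assume that the failure medians differ between arms by the planning mean differences. The SAP gives no gap for failures.

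- One affected dropout moves one arm mean by 3/600 = 0.005 or 6/600 = 0.01 lesion.
- With k such dropouts in each arm, the treatment difference shrinks by 2k/600 times the gap:

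| k per arm (assumed) | Inflammatory | Non-inflammatory |
|---|---|---|
| 1 | 0.01 | 0.02 |
| 6 | 0.06 | 0.12 |
| 12 | 0.12 | 0.24 |

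Even k = 12 is about a fifth of one SE (0.12/0.69 = 0.17; 0.24/1.15 = 0.21).

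**Donors, under either reading**

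- Observed failures per arm: 504·(1 − 0.23) ≈ 388 and 504·(1 − 0.15) ≈ 428.
- If the two arms' failure distributions have the same shape and differ by the gap, reclassifying one donor shifts a median by roughly gap/n. In the smaller pool this is 3/388 ≈ 0.008 or 6/388 ≈ 0.015 lesion.
- That median is given to at most about 600 − 504 = 96 subjects in the arm, so the arm mean moves by 0.16 times this, about 0.001 or 0.002 lesion per reclassified donor.

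**Never-treated subjects**

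The documents give no number. If 0.5% to 2% of the 1200 never apply drug (assumption), 0.005·1200 = 6 to 0.02·1200 = 24 subjects have no defined group under Reading A. Suppose, only to bound the effect, that 12 per arm were lost. Power at the planning values would go from 99.1% to 99.0% (inflammatory) and from 99.94% to 99.93% (non-inflammatory).

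**The case against.** The strongest reply is that the words about actual treatment attach only to calculating the median. The recipient clause does not repeat them, and in ITT and ITTT a subject's group is the randomized arm. This is a fair reading. It would remove the problem for wrong-product dropouts and never-treated subjects, but it leaves the donor medians on the wrong basis, and a prespecified rule should not need a choice between two readings.

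A reader might infer more than the documents support:

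- *Never-treated subjects fall out of the lesion analysis, so the co-primary endpoints are tested on different numbers.* No section excludes them. SAP 7.4.1.1 and 7.4.2.2 say that subjects with missing counts will be assigned a median. At most, their group is unspecified.
- *Every dispensing error puts a subject on the other arm.* SAP 5.5 lists such errors only as potential major deviations. A wrong kit may hold the same treatment. Drug is dispensed at Baseline, Week 4 and Week 8 (Protocol, Schedule of assessments), so one error need not settle a subject's actual treatment, which the documents do not define.
- *The example imputation code shows that the other analyses group subjects differently.* The treatment variable in that code is never defined in the documents, so nothing follows from its name.

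The objection that the effect is negligible also stands, as a statement about size. It does not remove the contradiction.

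**Conclusion.** The point holds as a minor correction. Addendum 6.6 calculates the medians on a basis that SAP 5.1 and 5.2 do not allow for ITT and ITTT. Because the addendum prevails over the SAP, the conflicting words are the ones in force. The donor problem is certain from the text. The recipient problem and the gap for never-treated subjects depend on reading the recipient clause as actual treatment.

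The likely effect is far below the standard error of the treatment difference. That conclusion rests on assumed counts of affected subjects and on using the planning differences as the gap between failure medians. It would be unwarranted to infer that the trial's ITT conclusions are compromised: one supportive analysis is affected, and the primary multiple-imputation analysis, power and type I error are untouched.

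**What to change.** In addendum 6.6, replace the reference to actual treatment with randomized treatment, and state that this applies both to calculating the median and to assigning it, on face and trunk. Add one sentence saying that randomized subjects who never applied study drug receive the median of their randomized group.

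The cost is a few words in the addendum and the matching grouping variable in the program. Sample size, power and alpha do not change, and there is no evident downside.
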